## C.2.10 Data Analysis

### Statistical Analysis

We will conduct descriptive analyses of measured variables, evaluate associations among variables, and changes over time. This review of the data will allow us to identify covariates (e.g. age groups, treatment regimen) that may require statistical adjustment in the final models. We will conduct exploratory analyses with baseline cross-sectional data using our de-identified data which may include emerging approaches to capture and analyze sleep and glucose metrics in this rapidly evolving area of research.

Our *overall statistical approach* will be a mixed-effect model for repeated measures (MMRM), recommended for primary analysis of clinical trials with continuous endpoints. Conceptually, MMRM is a more advanced version of repeated-measures ANOVA that can account for the correlation among multiple measurements over time, yet there is no assumption that participants are measured at every time point. Therefore, these models are very flexible at handling missing data. Participants who have a missing observation are not excluded; thus, this produces the intention to treat (ITT) full information maximum likelihood (FIML) model. While missing data will be minimized through careful procedures, some missing data are inevitable with longitudinal studies. We will handle missing data using the FIML approach that is appropriate for data missing at random. We will use inclusive models with auxiliary variables related to missingness among covariates collected at baseline, if needed, to support the missing at random assumption. Multiple imputation will be considered if excessive data are missing among predictor variables, e.g., change in sleep parameters for Aim 3. Sensitivity analyses such as pattern mixture models will be employed if data are suspected to be missing not at random.

**Aim 1:** Determine the effect of Sleep-Opt, compared to a healthy living attention control group, on the primary outcomes of sleep variability, sleep duration and glycemic control (A1C).

We will conduct MMRM using change from baseline for our primary outcome regressed onto categorical fixed effects for treatment arm, time, their interaction, and the initial baseline measure of the outcome. We will use an unstructured covariance structure to model within-person errors. If convergence problems occur, we will select the best fitting model from among several options, including random coefficients with residual covariance patterns such as autoregressive or exchangeable structure. In addition to A1C, we will estimate separate models for parameters from continuous glucose monitoring (glycemic variability, TIR). Sex will be included as a covariate and tested for moderation of the treatment effect. We will also control for BMI, A1C (for other glucose measures), and method of insulin delivery. If treatment arms are found to differ in the distribution of baseline characteristics despite randomization we will conduct sensitivity analyses including these variables as covariates. The primary endpoint will be change differences between groups at 12 weeks, based on least square means using a two-sided test with  $\alpha = .05$ . We will also assess differences in change from baseline to the 24-week endpoint to assess sustainability of effect.

**Aim 2:** Determine if Sleep-Opt will result in improved psychological and behavioral secondary outcomes, including diabetes distress, diabetes self-management behavior, and quality of life (QoL). Secondary outcomes will be analyzed with the same approach used in Aim 1.

**Aim 3:** Determine the contribution of changes in sleep variability and sleep duration during the intervention to changes in glycemic parameters (A1C, glycemic variability, TIR).

Sleep-Opt is designed to reduce sleep variability and extend sleep and duration, and we expect these changes to mediate change in glycemic control. In the context of the Aim 1 models, we will add time-varying sleep parameters, taking into account the average levels per person and the variation at each time point, to understand contributions of between- and within-person differences. We will also examine additional covariates predicting sleep parameters, because level and change in sleep parameters (while influenced by randomized treatment arm) are not experimentally controlled. In addition, we will test moderation of within-person mechanisms by sex, distress, method of insulin delivery, and A1C level using interaction terms. Successful completion of this aim will inform how aspects of sleep are related to the various aspects of glycemic control in general; which glycemic control parameters show reactivity to within-person fluctuations in sleep; and which personal characteristics may be more associated with this reactivity. This will explicate key mechanisms of change and suggest who may benefit most from sleep optimization.

As an additional statistical analysis we will explore the association of actigraphy-derived light and activity with sleep, glucose, and participant characteristics as ambient light may function as a covariate.

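### The adjustment covariates for the Aim 1 and Aim 2 models are not fixed in advance: three passages give different rules, and some listed covariates can arise after randomization

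*Combined protocol and SAP*

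**What the plan says.** Five places bear on which covariates enter the models.

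- **C.2.10, opening paragraph.** The team will "evaluate associations among variables, and changes over time", and this review will "allow us to identify covariates (e.g. age groups, treatment regimen) that may require statistical adjustment in the final models". No candidate list, threshold or blinding statement is attached.
- **C.2.10, Aim 1.** The model contains "treatment arm, time, their interaction, and the initial baseline measure of the outcome". Then: "Sex will be included as a covariate and tested for moderation of the treatment effect", and "We will also control for BMI, A1C (for other glucose measures), and method of insulin delivery". A separate clause covers chance imbalance: "If treatment arms are found to differ in the distribution of baseline characteristics despite randomization", the response is that "we will conduct sensitivity analyses including these variables as covariates". Aim 2 uses the same approach.
- **C.2.14, item 1.** Treatment modality, treatment changes and total daily insulin dose are to be collected for use as covariates in the primary-outcome analyses. None is restricted to its baseline value.
- **C.2.6.1 and section 3.1.** The first stratifies randomization by sex, A1C and age; the second by sex only.
- **Statistical Analysis Addendum.** Written before data analysis, it sets numeric thresholds for choosing auxiliary variables for missing data (0.20 and 0.30 in absolute value). For Aims 1 and 2 it refers back to the models already stated. It neither lists adjustment covariates nor withdraws the opening sentence of C.2.10.

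**The concern.** The opening paragraph sends data-identified covariates into the final models, the Aim 1 text gives a set that reads as complete, and C.2.14 gives a third list. Changes over time are outcome data, so the review can be informed by the endpoint. Age shows the gap: it is a stratification factor in C.2.6.1, it is absent from the Aim 1 model, and age groups are an example of what the data review may add.

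Two things are at stake. First, a reader of the Week 12 result could not tell whether the reported model was the planned one. Second, two particular uses of this freedom could damage the inference: choosing covariates with the treatment result in view, and adjusting for a variable that treatment itself changes. The second would also change the quantity being estimated, because part of the treatment effect may run through that variable.

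**Working it through.** **1. The plan's own figure.** C.2.5 gives 60 per group, two-sided alpha 0.02, 80% power and correlations of 0.5 to 0.8. For a change score, the detectable difference in SDs is (z₀.₉₉ + z₀.₈₀) × √(2/60) × √(2(1 − r)).

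- r = 0.5: (2.326 + 0.842) × 0.1826 × 1.000 = 0.578
- r = 0.8: (2.326 + 0.842) × 0.1826 × 0.632 = 0.366

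These match the stated 0.6 and 0.4, so the design inputs can be used below.

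**2. Does choosing baseline covariates from the data inflate type I error?** Setting: 60 per arm, no treatment effect, r = 0.7, change at Week 12 regressed on arm and baseline. The number of candidates is assumed, because the documents give none. There were 2,000 to 4,000 replicates, so the simulation standard error is √(0.05 × 0.95 / 4,000) = 0.003 to √(0.05 × 0.95 / 2,000) = 0.005. Nominal level 0.05:

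| Candidates | Fixed set | Chosen by association with outcome, ignoring arm | Chosen by imbalance, or by imbalance or association | Best single covariate by treatment p-value | Stepwise by treatment p-value |
|---|---|---|---|---|---|
| 5 | 0.054 | 0.052–0.053 | 0.055 | 0.066 | 0.074 |
| 10 | 0.045 | 0.046–0.049 | 0.044–0.047 | 0.068 | 0.094 |
| 20 | 0.050 | 0.049–0.051 | 0.052 | 0.078 | 0.172 |
| 10, three prognostic | 0.045 | 0.044–0.050 | 0.041–0.051 | 0.086 | 0.145 |

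Selection by association or imbalance stays at nominal within simulation error. Only selection on the treatment p-value exceeds it. At nominal 0.02, association rules give 0.017 to 0.024, best single 0.026 to 0.035, and stepwise 0.031 to 0.082.

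A second simulation (n = 120, 3,000 null trials per setting, independent prognostic covariates with standardized coefficient 0.2) kept the most favourable model. The best single covariate gave 7%, 8% and 9% with 2, 4 and 6 candidates. Free choice over all subsets gave 8%, 12% and 17%.

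**3. Adjusting for a variable measured after randomization.** Let a be the effect of arm on the covariate, in SDs, and c the correlation of the covariate with the part of the outcome that baseline does not explain. With no total treatment effect, the adjusted estimate is displaced by −a × c × √(1 − 0.7²) outcome SDs. With a = 0.4 and c = 0.5 this is −0.4 × 0.5 × 0.714 = −0.143. Simulated results (5,000 replicates):

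| a | c | Mean adjusted estimate (SD) | Type I error, nominal 0.05 |
|---|---|---|---|
| 0 | 0.3 to 0.5 | −0.001 to −0.002 | 0.054 |
| 0.2 | 0.3 | −0.044 | 0.063 |
| 0.2 | 0.5 | −0.073 | 0.096 |
| 0.4 | 0.3 | −0.084 | 0.103 |
| 0.4 | 0.5 | −0.144 | 0.236 |

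On the A1C scale, with the C.2.5 SD of 1.07%, the displacement runs from 0.044 × 1.07 = 0.05 to 0.144 × 1.07 = 0.15 percentage points. The planned difference in Table 4 is 7.8 − 7.4 = 0.4. Its direction depends on the signs of a and c. The values of a and c are assumptions. An arm effect on insulin dose is plausible on the protocol's own evidence, since C.1.1 reports a correlation of 0.386 between sleep variability and daily insulin requirement.

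**The case against.** The best defence is that the opening paragraph is a general preamble for all aims, including Aim 3, where further covariates are openly planned, and that the Aim 1 text is the specific rule. The imbalance clause has a different trigger from association, so the two can coexist. The examples are also not far-ranging: treatment regimen overlaps with insulin delivery, and age is a stratification factor. C.2.6.1 conceals allocation from most personnel.

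Much of this stands. A reader might infer that the primary model is wholly open. It is not: Aim 1 fixes its core terms. A reader might also infer that covariates will be picked with treatment results in view. No passage says so, and none plans selection on the treatment estimate or its p-value.

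The defence does not close the list. The preamble says final models without excluding Aims 1 and 2, C.2.14 speaks directly of the primary outcomes, and nothing says which passage governs. The concealment in C.2.6.1 exempts the project director and the investigators overseeing the two groups, and it is not tied to the covariate review.

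**Conclusion.** The point holds as a gap in prespecification: the adjustment set for Aims 1 and 2 is not closed, and the passages must be reconciled.

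The stronger conclusion, that the error rate exceeds its nominal level, is not supported. Choosing baseline covariates by association with the outcome, without regard to arm, is the nearest reading of the text, and it left error at 0.044 to 0.053. The 7% to 17% range is a hypothetical worst case under assumed candidate numbers and a rule the plan does not state. No bound specific to this trial can be derived, because the plan gives neither the candidates nor the criterion.

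The more concrete exposure is C.2.14, whose list includes variables that arise after randomization. The 6.3% to 23.6% range there rests on arm effects of 0.2 to 0.4 SD and correlations of 0.3 to 0.5; with no arm effect on the covariate, error stays at about 0.05.

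Two limits apply. The nominal level is itself inconsistent (0.02 in C.2.5, 0.05 in C.2.10 and the addendum). The addendum also reports 95% credible intervals, so error rates carry over to those only by analogy.

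**What to change.** Withdraw the covariate-review sentence in C.2.10 as it applies to Aims 1 and 2, and replace it, the Aim 1 list and C.2.14 item 1 with one closed list of adjustment covariates, all measured at baseline and fixed before unblinding:

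- arm, time, arm by time, and the baseline value of the outcome;
- the randomization factors, after reconciling C.2.6.1 (sex, A1C and age) with section 3.1 (sex only);
- BMI and method of insulin delivery, both at baseline;
- baseline A1C for the other glucose measures, as Aim 1 already intends.

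Covariates suggested by the descriptive review, and variables that arise after randomization (treatment changes, on-study insulin dose), should appear only in labelled sensitivity analyses. The existing imbalance clause can stay.

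The cost is SAP wording, with no new data and no change in sample size. The downside is that a strong prognostic covariate found later can be used only in a sensitivity analysis.

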**C.2.5 Sample size estimation.** We conservatively estimated the minimal detectable difference between treatment arms to be 0.4 to 0.6 standard deviations for our target sample size of 60 per group (after attrition) at the 12-week post-treatment measurement based on a 2-groups pre-post design,  $\alpha = 0.02$ , 2-sided, and 80% power. This represents a modest but clinically important change. Table 4 shows projected estimates for attention controls, based on our pilot data with this population, and the treatment group, based on the minimum detectable difference we could detect as statistically significant given our design, target sample size, and correlations between time points of 0.5 to 0.8. Standard deviations from pilot data for A1C (1.07%), sleep

variability (30 minutes), and sleep duration (49 minutes), and the correlation between measurements ( $r = 0.56$  to 0.85) were used for sample size determination.

Table 4. Minimum detectable treatment effects		
	Control	Treatment
A1C (%)	7.8	7.4
Sleep variability (minutes)	75	57
Sleep duration (minutes)	355	380

Analyses adjusting for the pre-treatment glucose level and other key covariates (e.g., BMI) will increase power. Aim 2 assesses the main effects of secondary outcomes and, similar to the primary aim, will allow us to detect effect sizes of 0.3 to 0.5 or greater as statistically significant. **Adjustment for multiple testing.** Our primary aim uses an adjusted alpha level for multiple primary outcomes. For secondary aims, exploratory, and hypothesis generating analyses we will publish unadjusted p-values and apply

the Benjamini-Hochberg approach to control the family-wise error rate. Aim 3 pertains to correlations between change measures of sleep and glucose control parameters, for which we will be able to detect correlations of the magnitude of .25 or greater as statistically significant.

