**C.2.8 Healthy Living Attention Control.** The research will be conducted remotely by phone call/video conference (Zoom) at participants' preference. The design of the 12-week control group is intended to control for the coach contact in the intervention group, so that we can test the intervention-related components (e.g. motivational enhancement, goal setting, feedback, and sleep education). [name] will train and oversee the coaches for the attention control group. Participants assigned to the health education control group will be provided eight scheduled emails with health education content (e.g. cooking, handwashing, stretching exercises; 8-10 minutes in length) with content written at the 4th grade level or below. Participants will receive eight brief (5- 10 min) telephone contact from the coach (see schedule Table 5) to determine if they received the information and if they had any questions about the materials. The schedule will mirror that of the intervention group. Coaches will not provide counseling or goal setting but may clarify terms or concepts. Participants in the healthy living control group will be instructed not to change their sleep behavior. They will be eligible to receive the sleep intervention at the end of the study. After the final follow-up session, they will receive a Fitbit wearable fitness tracker.

**C.2.9 Measures.** Self-report questionnaires will be used to obtain demographic, literacy, health information, menopausal status, food intake, psychological, behavioral and self-management characteristics (Table 6).

**C.2.9a Primary outcome and additional glycemic measures: Glycemic assessment.** 1.) Glycemic control will be assessed using hemoglobin A1C (A1C; Home Access Health Corp/Everlywell). A1C is a gold standard marker of glycemic control in T1D reflecting average glucose levels in the previous 90 days. 2) **Glycemic variability using CGM (blinded)** will be conducted using FreeStyle Libre Pro glucose sensor or Dexcom (FDA-approved). The sensor tracks glucose concentrations in the interstitial fluid over 24 h using a thin flexible filament (< 0.4 mm thick) inserted into the upper arm (5 mm depth). The system captures glucose levels every 1 minute and records the data every 15 minutes. Variables we will derive from the CGM are mean glucose level, standard deviation (SD), coefficient of variation (CV), percentage of time spent in range (70-180

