#### Statistical Analysis Addendum

Prior to data analysis the following are revisions were made to the analysis plan.

Multiplicity. The original proposal used alpha=.05 for 3 outcomes in the primary aim. We will use this threshold for all primary and secondary outcomes and provide a post hoc description of familywise error (e.g., families: sleep, CGM, psychosocial outcomes) using Holm's procedure.

Missing data approach. We will conduct our models for aims 1-3 (focal models) using an inclusive strategy incorporating extraneous auxiliary variables to support a conditionally missing at random assumption. We will examine missing data for all variables in our focal models. For variables with substantial missingness (5% or more) we will create a group indicator for missingness (yes, no) and examine effect sizes for extraneous baseline variables, considering those with effect sizes of  $>|.20|$  as being related to missingness. We will also consider extraneous baseline variables with partial correlations  $>|.30|$  with the variables with substantial missing. We will prioritize variables meeting both criteria, then those meeting only the partial correlation criteria. Variables only related to missingness will not improve the model and will not be considered further. Auxiliary variables will be included as additional outcomes in a way that does not affect interpretation of focal variables. If missing not at random is suspected, we will conduct pattern mixture or selection model approaches as sensitivity analyses. All models will be tested using BLIMP 3 software using Markov chain Monte Carlo estimation; we will report Bayesian median point estimates and 95% credible intervals for treatment effect estimates for previously stated models (i.e., MMRM) for aims 1 and 2 and mediation (indirect) effects from path models for aim 3 (see below).

Intention to treat and per protocol. Modeling for aims are based on the intention to treat principle retaining all individuals in their randomly assigned treatment arm. We will conduct per protocol models if more than 5% of participants did not adhere to the protocol, defined as completing at least 80% of sessions. In these models, we will assess for correlates of engagement and include them as control variables in models excluding the participants who did not complete the protocol.

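### The Aim 1 and Aim 2 models include baseline only as a main effect, so one baseline slope serves Weeks 6, 12 and 24; a baseline-by-time term is a cheap, minor improvement, chiefly for A1C

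*Combined protocol and SAP*

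**What the plan says.** C.2.10, Aim 1, specifies an MMRM in which change from baseline is "regressed onto categorical fixed effects for treatment arm, time, their interaction, and the initial baseline measure of the outcome". Sex, BMI and method of insulin delivery are added as covariates. On the residuals: "We will use an unstructured covariance structure to model within-person errors". On the estimand: "The primary endpoint will be change differences between groups at 12 weeks, based on least square means", with Week 24 as a further contrast for sustainability. Aim 2 uses the same approach.

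The Statistical Analysis Addendum moves estimation to Bayesian MCMC but keeps the model: it will report "credible intervals for treatment effect estimates for previously stated models (i.e., MMRM) for aims 1 and 2". Neither C.2.10 nor the addendum lets the baseline effect vary by visit.

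Two other places bear on the point. C.2.5 plans on "correlations between time points of 0.5 to 0.8" and cites a pilot range of 0.56 to 0.85; neither range is broken down by visit. C.2.9a describes A1C as "reflecting average glucose levels in the previous 90 days".

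**The concern.** With baseline as a main effect only, the regression of change on baseline is the same at every post-baseline visit. An unstructured covariance does not relax this, because it describes the residuals and not the mean. If baseline predicts Week 6 better than Weeks 12 and 24, the fitted slope is a compromise pulled toward the best-predicted visit, and it is wrong at the primary time point.

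Two things are at stake. The misfit at Week 12 goes into the residual variance and widens the interval. In addition, the plan's protection under missing at random requires a correct mean model. If the patients still observed at Week 12 differ in baseline between arms, a wrong slope adjusts for that difference wrongly and part of it leaks into the treatment contrast.

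**Working it through.** **1. The plan's own figure.** Inputs from C.2.5: 60 per group, two-sided alpha 0.02, power 80%, correlation r from 0.5 to 0.8. The change-score formula in SD units is MDD = (2.326 + 0.842) × √(2/60) × √(2(1 − r)).
- r = 0.5: 3.168 × 0.1826 × 1.000 = 0.578
- r = 0.8: 3.168 × 0.1826 × 0.632 = 0.366

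These round to the stated 0.6 and 0.4 SD, so the planning figure reproduces. It uses the change-score variance 2(1 − r), with no gain from baseline adjustment.

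**2. Should the A1C correlation fall?** With the 90-day window and equal weighting of days (an assumption), the share of each value that predates the program is:
- Week 6: (90 − 42)/90 = 53%
- Week 12: (90 − 84)/90 = 7%
- Week 24: 168 days exceed 90, so 0%

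A fall is therefore expected for A1C, but its size is not given. The actigraphy outcomes come from separate one-week recordings with no such overlap.

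**3. Precision.** Take unit variances at all visits (assumed). Let r₆, r₁₂, r₂₄ be the baseline correlations and S the residual covariance of the three visits given baseline. The common slope converges to b = 1′S⁻¹r / 1′S⁻¹1. The standard-error ratio at visit t, common over visit-specific, is √[(1 − r_t² + (r_t − b)²)/(1 − r_t²)].

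Example: baseline correlations 0.85/0.70/0.56 with between-visit correlations 0.85 (6–12), 0.70 (6–24) and 0.85 (12–24) give b = 0.820.
- Week 12: √[(0.510 + 0.0144)/0.510] = 1.014
- Week 24: √[(0.6864 + 0.0676)/0.6864] = 1.048

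| Baseline r at Weeks 6/12/24 | Between-visit r (6–12, 6–24, 12–24) | b | Week 12 SE | Week 24 SE |
|---|---|---|---|---|
| 0.7/0.7/0.7 | 0.7, 0.7, 0.7 | 0.70 | +0% | +0% |
| 0.8/0.7/0.6 | 0.8, 0.7, 0.8 | 0.75 | +0.2% | +1.7% |
| 0.8/0.65/0.5 | 0.8, 0.65, 0.8 | 0.746 | +0.8% | +4.0% |
| 0.85/0.70/0.56 | 0.85, 0.70, 0.85 | 0.820 | +1.4% | +4.8% |
| 0.85/0.56/0.56 (abrupt) | 0.6, 0.6, 0.6 | 0.764 | +3.0% | +3.0% |
| 0.85/0.56/0.56 (abrupt) | 0.7, 0.7, 0.7 | 0.808 | +4.4% | +4.4% |
| 0.85/0.56/0.56 (abrupt) | 0.85, 0.70, 0.85 | 0.980 | +12.1% | +12.1% |

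Over a grid of non-increasing baseline correlations, with between-visit correlations in the same range, the Week 12 widening has median 0.1% and 95th percentile 2.2% (range 0.5–0.8), or 0.1% and 3.5% (range 0.56–0.85). The grid's largest values come from extreme, near-degenerate correlation patterns.

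In power terms, a test with exactly 80% under visit-specific slopes would have about 79.3%, 78.8% or 76% when the standard error is 0.8%, 1.4% or 4.4% wider.

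**4. Bias.** Both models were fitted by maximum likelihood to 300,000 simulated patients with monotone dropout. Total dropout was 17% (C.2.11) or 1 − 120/170 = 29.4% (implied by C.2.3). Assumed: a logit dropout slope of 1.0 per baseline SD, and dropout split 30/40/30% before Weeks 6, 12 and 24. A1C points are SD units × 1.07.

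| Dropout depends on baseline | Gradual fall (0.8/0.65/0.5; 0.85/0.70/0.56) | Abrupt fall (0.85/0.56/0.56) |
|---|---|---|
| equally in both arms | about 0 | about 0 |
| in one arm only | 0.012–0.024 SD = 0.01–0.03 points | 0.027–0.041 SD = 0.03–0.04 points |
| in opposite directions by arm | 0.026–0.044 SD = 0.03–0.05 points | 0.053–0.081 SD = 0.06–0.09 points |

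With visit-specific slopes the residual is at most 0.005 SD, which is simulation error. Table 4's A1C difference is 7.8 − 7.4 = 0.4 points, or 0.4/1.07 = 0.37 SD.

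**The case against.** The strongest reply is that the effect is usually negligible and rests on correlations the plan never gives. Much of that stands. A reader might infer that the ranges in C.2.5 themselves show a decline over time. They do not: they are planning ranges stated alongside the SDs of three different outcomes, and the T1D pilot in C.1.4 measured at Weeks 0, 8 and 12, so it has no Week 6 or Week 24 value. A reader might also extend the argument to all three primary outcomes, but the 90-day window concerns A1C only.

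A further tempting reading is that any dropout related to baseline biases the Week 12 contrast. The simulation shows about zero bias when the dependence is the same in both arms. Dropout that differs by arm is possible, since one arm gets goal setting and tracking and the other is told not to change its sleep behavior, but the documents do not predict it.

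Finally, one might infer that the study loses its planned power. It does not, because planning used the larger change-score variance. At r₁₂ = 0.65 the common-slope variance is 0.5775 + 0.0092 = 0.587, against 2(1 − 0.65) = 0.70. In the abrupt case with between-visit correlations of 0.7 it is 0.748 against 0.88.

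What the reply does not remove is the omission itself. As written the slope is common, and freeing it costs almost nothing even if the slopes turn out equal.

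**Conclusion.** The point holds as a minor specification improvement. The common slope is clear from the text. A visit-varying slope is expected for A1C and uncertain for sleep duration and sleep variability.

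For a gradual fall within the plan's ranges, the Week 12 standard error is about 0–1.5% wider in the scenarios tabulated; less regular between-visit correlations can raise this to about 3.5%. For an abrupt fall it is roughly 3–12%. At Week 24 the gradual-fall cost is about 1–5%, so the sustainability contrast loses more than the primary one.

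Bias in the Week 12 A1C contrast is about 0.01–0.05 points for a gradual fall and at most about 0.09 for an abrupt one, that is up to 0.05/0.4 = 12% and 0.09/0.4 = 22% of the Table 4 difference. It arises only with dropout that depends on baseline differently by arm.

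These sizes rest on assumed visit-specific correlations, equal variances over time, and the assumed dropout strength and timing. Confidence is high for the omission and low for the upper magnitudes. The 0.4 to 0.6 SD planning figure stands.

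**What to change.** Before analysis, add a baseline-by-time interaction to the Aim 1 model in C.2.10, and hence to Aim 2 and the addendum: change = arm + time + arm × time + baseline + baseline × time + listed covariates, with unstructured covariance. Keep the term if the convergence fallback is used. The Week 12 contrast is already named as the primary endpoint, so that wording can stay.

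The cost is one line of text and two extra parameters per model (three post-baseline visits minus one), with a negligible loss of degrees of freedom and no new data. It should be settled before results are seen by arm; added later, it would be a post hoc choice about the primary estimate.
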